12 PATIENT DISPOSITION

12.1 Removal of Patients from the Study or Study Drug

A patient must be discontinued from protocol prescribed- therapy if any of the following apply:

- Consent withdrawal for any reason at the patient's own request or at the request of their legally authorized representative;
- Radiographic progression of patient's underlying cancer per modified RECIST Version 1.1/PCWG3 (unless, in the opinion of the investigator, the patient continues to derive clinical benefit; treatment beyond progression is permitted with additional consent);
- Unequivocal clinical progression of the patient's underlying cancer that in the opinion of the investigator requires immediate change in systemic anticancer therapy, or results in marked deterioration in ECOG performance status to Grade 3 or higher
- Any event, adverse or otherwise, that, in the opinion of the investigator, would pose an unacceptable safety risk to the patient;
- An intercurrent illness that, in the opinion of the investigator, would affect assessments of the clinical status to a significant degree and requires discontinuation of therapy;
- Noncompliance by the patient with protocol mandated procedures

Discontinuation of treatment does not necessarily indicate study discontinuation for a patient. Samples collected for research will continue to be used unless the patient explicitly withdraws consent for their use. If the patient withdraws consent to continue in the study or discontinues the study for another reason it will be documented on the appropriate eCRF. A patient may withdraw consent to participate in an additional part of a study that has an additional consent (ie, optional tumor biopsy) yet continue to participate and be treated/ followed in the main part of the study.

The sponsor may discontinue the trial early for any of the reasons noted in [Section 13.7](#).

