5.1.4 Post-treatment Phase

The sponsor (or designee) should be notified of all treatment terminations as soon as possible. The date and reason for cessation of study drug must be documented in the eCRF and source documents. Patients will undergo procedures and assessments during the Post-treatment Phase as described in [Section 9.6](#). Upon treatment discontinuation, patients will have a Treatment Discontinuation Visit ([Section 9.6.1](#)), a 28-Day Follow-up Visit ([Section 9.6.2](#)), and then will proceed to long-term follow-up ([Section 9.6.3](#)). An optional tumor biopsy will be collected prior to the start of subsequent anticancer therapy from patients who experience radiographic or unequivocal clinical disease progression and who provide appropriate consent. For patients who had their last tumor assessment ≥ 8 weeks (≥ 12 weeks if previous scan was after 24 weeks on study) prior to Treatment Discontinuation Visit, a tumor assessment must be performed.

If treatment was discontinued for reasons other than radiologic disease progression, radiologic tumor assessment (using the same methodology as was used at initial study screening [eg, CT scan]) and PRO assessments will continue until confirmed radiographic disease progression. For these patients, tumor assessments should continue to be performed at the end of every 8 calendar weeks (± 7 days) relative to Study Day 1 (Week 1) up to 24 weeks and then every 12 calendar weeks (± 7 days) thereafter, until confirmed radiologic disease progression by modified RECIST Version 1.1 and PCWG3 (for bone lesions only) criteria as assessed by the investigator, loss to follow-up, withdrawal of consent, or study closure. For patients who start subsequent

anticancer therapy, tumor assessments will continue until radiologic disease progression is confirmed.

Ongoing SAEs, AESIs, and treatment related Grade 3/4 AEs will be followed until either resolution or stabilization has been determined or until loss to follow-up. After the 28-Day Follow-up Visit, only SAEs considered as potentially related to study drug should be reported per Clovis Pharmacovigilance (PV) requirements and captured in the Clovis PV database. This includes serious reports of pneumonitis or associated events, if considered to be related to study drug.

After the 28-day Follow-up Visit, AESIs of MDS and AML, irrespective of causality, should be reported per Clovis PV requirements and captured in the Clovis PV database.

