- ^k = Disease assessment by CT/MRI and bone scans will be performed during screening, during the treatment phase, and Treatment Discontinuation, and if applicable, during follow up. Modified RECIST 1.1/PCWG3 criteria will be used. If a CR or PR is noted, confirmatory scans should be performed at least 4 weeks after the initial response was first documented.

- ^l = Radiologic assessments should continue for all patients until confirmation of radiographic progression per investigator assessment, including any patient who discontinued from study treatment for reason other than disease progression or death. Tumor assessments should be performed during the Treatment Discontinuation visit, 28-day Follow-up, or during Long-term Follow-up if the reason was other than radiologically confirmed disease progression and it has been ≥ 8 weeks (≥ 12 weeks if previous scan was after 24 weeks on study) since the last assessment. Tumor assessments should continue on schedule (ie, every 8 or 12 weeks) during Long-term Follow-up until radiographically confirmed disease progression.
- ^m = If archival primary or metastatic tumor tissue was not submitted during Pre-Screening, a specimen should be submitted during the Screening period or after enrollment for retrospective testing by the central laboratory. Archival tissue submitted during Screening for retrospective testing can be > 3 years old. Refer to the Pathology Charter for detailed sample handling instructions.
- ⁿ = The BPI-SF, analgesic drug score, FACT-P, and EQ-5D-5L instruments should be completed prior to other scheduled study procedures and dosing (if applicable). During long term follow up, if possible, PROs to be collected to coincide on days when tumor assessments are performed.
- ^o = All PSA measurements are performed by the local laboratory. Serial PSA measurements that show progression at study entry must follow the protocol specification.

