9.6 Post-treatment Phase

9.6.1 Treatment Discontinuation Visit

Upon treatment discontinuation, regardless of the reason, patients will have a Treatment Discontinuation Visit. However, patients receiving rucaparib with radiologic disease progression by modified RECIST Version 1.1 and/or PCWG3 criteria (for bone lesions), as assessed by the investigator, but still receiving benefit, per the investigator, may be considered for treatment continuation. Continuation of rucaparib treatment beyond progression will require separate patient consent. If the patient does continue to receive rucaparib, then the patient will continue treatment with rucaparib as described starting in [Section 9.5.5](#) and a Treatment Discontinuation Visit will occur at the end of all rucaparib treatment. Patients who continue treatment with rucaparib after radiologic disease progression will have the option of tumor tissue biopsy collection at time of first disease progression on study (requires additional consent). Tumor tissue will be processed locally as formalin-fixed paraffin-embedded (FFPE) tissue. Refer to the Pathology Charter for detailed sample handling instructions.

The following procedures will be performed:

- PRO collected using the BPI-SF ([Appendix 6](#)), FACT-P ([Appendix 7](#)), EQ-5D-5L ([Appendix 8](#)), and analgesic drug score instruments ([Appendix 9](#); should be completed before other procedures)
- Physical examination
- Weight
- Vital signs
- 12-lead ECG

- Tumor assessment if it has been ≥ 8 weeks (≥ 12 weeks if previous scan was after 24 weeks on study) since the last assessment and the reason for treatment discontinuation was other than radiographically confirmed disease progression.
- Concomitant medications and procedures
- ECOG performance status ([Appendix 3](#))
- PSA measurement
- Hematology
- Serum chemistry (fasting is not required)
- Urinalysis
- Plasma sample for ctDNA
- AE (inclusive of SAE and AESI) monitoring
- Optional tumor tissue biopsy collection after the time of disease progression (radiologic or clinical) and prior to initiation of any subsequent anticancer therapy (requires additional consent). Tumor tissue will be processed locally as FFPE tissue. Refer to [Section 9.11](#) for more information and to the Pathology Charter for detailed sample handling instructions.

9.6.2 28-Day Follow-up Visit

The following procedures will be performed for all patients at 28 (± 3) days after the last dose of rucaparib.

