- PRO collected using the BPI-SF ([Appendix 6](#)), FACT-P ([Appendix 7](#)), EQ-5D-5L ([Appendix 8](#)), and analgesic drug score instruments ([Appendix 9](#); should be completed before other procedures)
- Physical examination
- Weight
- Vital signs
- Tumor assessment only if it has been ≥ 8 weeks (≥ 12 weeks if previous scan was after 24 weeks on study) since the last assessment for those patients that have not had radiographic progression confirmed by investigator assessment
- Concomitant medications and procedures
- ECOG performance status ([Appendix 3](#))
- Hematology
- Serum chemistry (fasting is not required)
- Urinalysis
- AE (inclusive of SAE and AESI) monitoring

- Information collected for subsequent treatments.

Patients who do not withdraw from the study at this visit will continue with long-term follow-up as described in [Section 9.6.3](#).

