10.1 Primary Efficacy Analysis

For Cohort A, the primary efficacy endpoint is confirmed radiographic ORR by central IRR (as described in [Section 9.1](#)) in patients with measurable visceral and/or nodal disease at baseline. To be considered a responder at a specific time point, a patient must have a CR or PR assessment per modified RECIST and no confirmed bone progression per PCWG3 on or prior to a CR or PR. To be considered a confirmed responder, a patient must have at least 2 responses at least 4 weeks apart prior to a modified RECIST/PCWG3 progression event.

Confirmed radiographic ORR will be summarized with frequencies and percentages along with 95% confidence intervals. The frequency and percentages of patients with a best overall response of complete response (CR), partial response (PR), stable disease (SD), or progressive disease (PD) will also be summarized.

An analysis of confirmed radiographic ORR by the investigator will also be conducted as supportive to the primary endpoint and will use the Investigator Efficacy Population (patients evaluable for response by modified RECIST/PCWG3 criteria per investigator).

For Cohort B, the primary efficacy endpoint is confirmed PSA response as assessed by a local laboratory in patients without measurable disease at baseline (by central IRR). Confirmed PSA response is defined as having 2 consecutive PSA values (at least 3 weeks apart) that are at least 50% lower than baseline and that occur prior to PSA progression (as defined in [Section 10.2.6](#)). Per PCWG3, early rises (before 12 weeks following first dose of study drug) in PSA should be ignored when determining PSA response. Confirmed PSA response will be calculated for patients with PSA values at baseline.

Confirmed PSA response will be summarized separately, with frequencies and percentages along with 95% confidence intervals, for patients without measurable disease per IRR (primary endpoint) and without measurable disease per Investigator (supportive analysis). PSA response will also be summarized for patients with measurable disease (both IRR and Investigator, separately) and for all patients.

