10.2.6 Time to PSA progression

Time to PSA progression is defined as the time from first dose of rucaparib to the date that a $\geq 25\%$ increase and absolute increase of ≥ 2 ng/mL above the nadir (or baseline if there was no PSA decline after baseline) in PSA was measured, plus 1 day. The increase must be confirmed by a second consecutive assessment conducted at least 3 weeks later (unless the PSA progression occurred at the last recorded PSA assessment). If confirmed, the date used for time of PSA progression is the earlier of the 2 PSA dates. Additionally, early rises (before 12 weeks following first dose of study drug) are not considered in determining PSA progression.

Time to PSA progression will be summarized for all patients and may also be summarized for the subgroups of patients defined by measurable disease status at baseline.

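### No PSA is scheduled after the Treatment Discontinuation Visit, so a 50% PSA fall first seen at that visit, or fewer than 21 days before it, has no scheduled value that can confirm it

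*Protocol*

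**What the plan says.** **Schedule.** Table 5 places PSA at Screening, Day 1, Day 29, Day 57 and every 28 days from then on, and at Treatment Discontinuation. Footnote o adds only that "All PSA measurements are performed by the local laboratory". Section 9.6.1 lists PSA for the discontinuation visit. Section 9.6.2 opens with "The following procedures will be performed for all patients at 28 (± 3) days after the last dose of rucaparib". Its list includes hematology, serum chemistry and urinalysis but not PSA, and the chemistry panel in 9.10.2 does not contain it either. Section 9.6.2 ends by saying "Patients who do not withdraw from the study at this visit will continue with long-term follow-up"; the long-term list in 9.6.3 has scans, questionnaires, survival, later treatments and safety reports, again without PSA.

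**Other assessments after a stop.** Section 12.1 separates leaving treatment from leaving the study: "Discontinuation of treatment does not necessarily indicate study discontinuation for a patient". Section 5.1.4 reads "If treatment was discontinued for reasons other than radiologic disease progression, radiologic tumor assessment" and has these scans, with the questionnaires, run until radiographic progression is confirmed.

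**Endpoint.** For Cohort B, and for Cohort C patients without measurable disease, the primary endpoint is confirmed PSA response. SAP 10.1 defines it as "having 2 consecutive PSA values (at least 3 weeks apart) that are at least 50% lower than baseline", before PSA progression. On the denominator it says "Confirmed PSA response will be calculated for patients with PSA values at baseline". SAP 11.1 rules out imputation. For PSA progression, SAP 10.2.6 requires confirmation "unless the PSA progression occurred at the last recorded PSA assessment". SAP 10.1 has no matching provision for a fall.

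**The concern.** The assessment that decides the primary endpoint in these patients ends earlier than the scans and questionnaires, although the endpoint needs a second value 21 days or more after the first. If treatment stops soon after a first 50% fall, the plan schedules nothing that could show whether the fall held. The patient stays in the denominator and is scored as a nonresponder because a sample is absent, not because a later PSA rose. Cohort A is better placed: after a non-radiographic stop its scans go on, so a confirming scan can still be obtained.

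At stake is the accuracy of a primary response rate that is judged against a fixed cut-off.

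**Working it through.** **1. The plan's own figures.** Inputs from Protocol 11.7 and SAP 2.3: Cohort B (BRCA1/2) continues with at least 5 of 19 and rejects 20% with at least 16 of 54; Cohort B (ATM) continues with at least 5 of 18 and rejects with at least 11 of 33. With n1 and n the stage 1 and total sizes, r1 the largest count that triggers the futility review, and r the rejection count:

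P(reject | p) = Σ over x > r1 of Bin(x; n1, p) × P(Y ≥ r − x), with Y ~ Bin(n − n1, p).

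| Sub-cohort | p = 20% | p = 40% | Stated |
|---|---|---|---|
| BRCA1/2 | 0.0482 | 0.9045 | 5%, 90% |
| ATM | 0.0458 | 0.8011 | 5%, 80% |

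The stated design figures are reproduced. The point concerns the schedule only.

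**2. While treatment continues there is no gap.** Visits are 28 days apart, each with a ±3-day window (Table 5, footnote a). Two consecutive visits are therefore 28 − 6 = 22 to 28 + 6 = 34 days apart, always at least 21.

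**3. At a stop.** Let s be the days from the first fall to the stop. If the discontinuation visit is held then, or up to 3 days later, its PSA comes s to s + 3 days after the fall.
- s ≤ 17: the gap is at most 20 days, so it cannot confirm.
- s = 18 to 20: it confirms only if the visit is held late enough to reach 21 days.
- s ≥ 21: it can confirm.
- Fall first seen at the visit itself (s = 0): no later value is scheduled.

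The earliest regular on-treatment PSA is Day 29 − 3 = 26, and 26 + 21 = 47. A patient whose discontinuation visit falls before Day 47 cannot be a confirmed responder on scheduled samples.

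**4. Effect of the dose-hold rule.** Protocol 7.4.2 ends treatment if a toxicity hold exceeds 14 consecutive days, unless investigator and sponsor agree otherwise. If the hold starts h days after the fall, a stop under this rule comes no earlier than h + 15 days after it. Then h + 15 ≥ 21 when h ≥ 6. Example: fall on Day 29, hold from Day 36, stop on Day 51; 51 − 29 = 22 days, so the discontinuation PSA can confirm. A hold starting 1 day after the fall gives 16 days at the earliest, which is too soon.

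**5. Would a PSA at the 28-Day Follow-up Visit close the gap?** That visit is 25 to 31 days after the last dose.
- Fall seen on or before the last dose: the gap is at least 25 days, so it qualifies.
- Fall first seen at a discontinuation visit d days after the last dose: the gap is 25 − d to 31 − d. It is certain to reach 21 only if d ≤ 4. At d = 15 it is 10 to 16 days, too short.
- Split pair: suppose the fall is seen on the last-dose day, a discontinuation PSA is taken T days later, and the follow-up PSA is taken at day 28. Neither adjacent pair reaches 21 days when T < 21 and 28 − T < 21, that is, T = 8 to 20. The outer pair is 28 days apart, but a strict reading of *consecutive* rejects it.

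**6. Size of one patient.** 1/54 = 1.9 and 1/33 = 3.0 percentage points; at full enrolment 1/100 = 1.0 and 1/50 = 2.0. Sixteen of 54 rejects the null and 15 of 54 does not.

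**7. Denominator.** The affected patient has a baseline PSA and at least one later PSA. He is therefore counted under SAP 10.1 and also under the protocol's 11.5.2, which asks for one post-baseline value.

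**The case against.** The best case for the plan is that requiring confirmation, and counting unconfirmed patients as nonresponders, is a deliberate and conservative choice in a single-arm trial. An unconfirmed fall is not a response, and some would not have lasted. The affected group is small: first fall shortly before a stop, or first seen at it. Many toxicity stops follow a hold of more than 14 days, which often makes the discontinuation PSA late enough. PSA is a local test, nothing bars an unscheduled one, and it could rescue the patient. Cohort B also reports rates with 95% confidence intervals, calls its rule a futility rule, and may enrol about 100 and 50, where one patient matters less.

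All of this stands as a limit on weight. It does not supply the missing sample: neither document asks for an unscheduled PSA, and a short interval before the stop, with or without a hold, still leaves the fall untested.

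A reader might go further and infer a loss of power. The documents do not support that. They give no early-stop rate in this disease. The stop data in Protocol 3.4.2.3 come from ovarian cancer, and a treatment duration there reflects stops for every reason, including progression, which is unlikely just after a 50% PSA fall. The 40% in the design is described only as the rate for an effective drug; if it already describes the endpoint with early stoppers as nonresponders, nothing is lost.

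**Conclusion.** The point holds as a narrow schedule gap. It follows from Table 5 and 9.6.1 to 9.6.3 read with SAP 10.1, and applies to Cohort B and to PSA-assessed Cohort C patients. Its direction is against the drug. Its total size is unknown because the number of affected patients cannot be derived from the documents; only the weight of one patient can.

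The day counts assume that the discontinuation visit is held at the stop or within 3 days of it, and that no unscheduled PSA is taken.

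Two further inferences should be resisted. One is that section 12.1 is at fault: its sentence is correct and only shows that these patients remain available for a further sample. The other is that the reported rate is known to be too low: the plan leaves some falls untested, which is not the same as showing that they were lasting responses. The priority is low, but the remedy costs so little that it is worth making.

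**What to change.** 1. **Protocol 9.6.2 and Table 5.** Add a local PSA at the 28-Day Follow-up Visit for patients not yet on new anticancer therapy. If a 50% fall is first seen at a discontinuation visit more than about 4 days after the last dose, that sample may be too early; ask then for a local PSA at least 21 days after the fall and before new therapy.
2. **SAP 10.1.** Accept as confirmation any PSA at least 21 days after the first fall that is still at least 50% below baseline, precedes subsequent anticancer therapy (the limit that SAP 10.2.2 sets for scans), and has no value in between above that level. A discontinuation PSA then no longer splits the pair.
3. **Reporting.** Count the Cohort B and PSA-assessed Cohort C patients with a 50% fall and no PSA at least 21 days later. Give a sensitivity response rate that treats them as responders. The primary rate continues to count them as nonresponders.

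The cost is one local assay at a visit where blood is already drawn, one eCRF field and short protocol and SAP text. The exception is the late-discontinuation case in item 1, which may need a separate local draw.

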13 STUDY ADMINISTRATION

13.1 Regulatory and Ethical Considerations

13.1.1 Good Clinical Practice

This study will be conducted in accordance with the protocol and applicable standard operating procedures (SOPs); and in compliance with applicable regulations and guidelines including;

- International Council for Harmonisation (ICH) E6 (R2);
- The Code of Federal Regulations (21 CFR Parts 11, 50, 54, 56, and 312);
- European Union (EU) Directive 2001/20/EC, 2003/94/EC, 2005/28/EC, 536/2014 and
- All applicable local requirements, and in accordance with the ethical principles of the Declaration of Helsinki.

The investigator will assure that no amendments to the protocol will take place without prior agreement from the sponsor and documented approval from the IRB/IEC, and local health authority (where applicable), except where necessary to eliminate an immediate hazard(s) to the study participants.

Significant noncompliance with the protocol, SOPs, Good Clinical Practice (GCP), and/or applicable regulatory requirement(s) by an investigator/institution, or by member(s) of the sponsor staff or its representatives will lead to prompt action by the sponsor to secure compliance. If monitoring and/or auditing identifies serious noncompliance on the part of an investigator/institution, the sponsor will take steps to secure compliance or terminate the investigator's/institution's participation in the study. When an investigator's/institution's participation is terminated because of significant noncompliance, the sponsor will promptly notify the regulatory authority(ies) and other appropriate parties (eg, IEC/IRB).

All potential serious breaches of GCP must be reported to the sponsor or designee within 24 hours. A serious breach is a breach of the conditions and principles of GCP in connection with the study or the protocol, which is likely to affect, to a significant degree, the safety or physical or mental integrity of the participants of the study or the scientific value of the study.

Personnel involved in conducting this study will be qualified by education, training, and experience to perform their respective tasks.

This study will not use the services of study site personnel where sanctions have been invoked or where there has been scientific misconduct (eg, debarment).

